11.0 TOXICITIES/SIDE EFFECTS

The patients will be evaluated every 28 days before initiation of a new cycle of treatment. All toxicities with a maximum grade and status of \geq grade 2 will be graded using the Common Terminology Criteria for

MEMORIAL SLOAN-KETTERING CANCER CENTER
IRB PROTOCOL

IRB#: 11-107A(12)

Adverse Events (CTCAE) Version 4.0.

11.1 Expected Side Effects of Lenalidomide

Most frequently reported adverse events reported during clinical studies with lenalidomide in oncologic and non-oncologic indications, regardless of presumed relationship to study medication include the following:

Likely:

- Feeling tired (fatigue)
- Loss of strength (asthenia)
- Loose, frequent bowel movements (diarrhea)
- Difficulty moving bowels (constipation)
- Altered sense of taste (dysgeusia)
- Nose bleed (epistaxis)
- Decrease in red blood cells that can cause tiredness (anemia)
- Decrease in white blood cells that can make you more prone to infections (neutropenia)
- Decrease in platelets which can cause you to bruise or bleed easily (thrombocytopenia)
- Blurred vision
- Abnormal sense of touch
- Pain and decreased sensation in nerves

Less Likely:

- Fever
- Problem with moving food through digestive system (gastrointestinal motility disorder)
- Weight loss, loss of appetite
- Dry mouth
- Nausea
- Vomiting
- Chills
- Indigestion (dyspepsia)
- Muscular weakness
- Stroke
- Tingling sensation (paresthesia)
- Swelling or edema (including peripheral)
- Itching and dry skin (pruritis)
- Rash
- Sores on the skin (pyoderma gangrenosum)
- Cough
- Shortness of breath (dyspnea)
- Fainting (syncope)
- Dizziness
- Drowsiness
- Headache
- Difficulty sleeping (insomnia)
- Bleeding
- Difficulty breathing (respiratory distress)

MEMORIAL SLOAN-KETTERING CANCER CENTER IRB PROTOCOL

IRB#: 11-107A(12)

Excessive sweating (hyperhidrosis)
Fever with a decrease in white blood cells that help fight infections (febrile neutropenia)
Shortage of all types of blood cells including red blood cells, white blood cells, and platelets (pancytopenia)
Infection, especially when white blood cell count is low
Blood clots (thromboembolic event)
Excessive loss of body water (dehydration)
High blood sugar (hyperglycemia)
Uncontrolled blood sugar (diabetes mellitus)
Higher than normal blood uric acid (hyperuricemia)
Higher than normal level of iron in body (iron overload)
Lower than normal level of thyroid hormone (hypothyroidism)
Lens of eye becomes cloudy (cataracts)
High blood pressure (hypertension)
Low blood pressure (hypotension)
Joint pain (arthralgia)
Back pain
Muscle pain (myalgia)
Muscle cramp / spasm
Altered mood
Depression
Irregular heartbeat (atrial fibrillation)
Failure of the heart (cardiac failure)
Heart attack (acute myocardial infarction)
Fast heartbeat (tachycardia)
Not enough blood flow to heart muscle (myocardial ischemia)
Kidney damage (renal failure)
Abnormal liver function tests

Rare but Serious

Fever with a decrease in white blood cells that help fight infections (Febrile neutropenia)
Blood clot in or around the lungs (Pulmonary embolism)
Deep vein thrombosis or blood clots in larger blood vessels
Atrial fibrillation or irregular heartbeat
Pneumonia or an infection of the lungs
Sepsis or an infection of the blood
Inflammation of the pancreas, which causes increase in pancreatic enzymes (lipase), which could result in abdominal pain and discomfort
Allergic reaction which may cause rash, low blood pressure, wheezing, shortness of breath, swelling of the face or throat (anaphylaxis)
Kidney failure or inability of the kidneys to remove waste from the body
Muscle breakdown (rhabdomyolysis)
Swelling of the lungs
Severe skin rash with blisters that can involve the inside of the mouth and other parts of the body (erythema multiforme)
Serious allergic skin reactions that begin as a rash in one area and later cover more of the body, leading to separation of the top layer of skin (Stevens- Johnson syndrome /

MEMORIAL SLOAN-KETTERING CANCER CENTER IRB PROTOCOL

IRB#: 11-107A(12)

toxic epidermal necrolysis)

Damage to organs in the body when donor cells attack host organs, which may cause yellowing of the eyes and skin, itchy dry skin, or muscle weakness (Graft versus host disease)

Complications caused by the break-down products of dying cancer cells, which can include high potassium, high phosphorous, high uric acid in the blood and urine, low calcium, and can result in kidney damage (Tumor lysis syndrome)

Cancer of bone marrow caused by chemotherapy

A new cancer resulting from treatment of earlier cancer

Low blood cell counts that may cause infection, anemia, spontaneous bleeding, or easy bruising (Myelodysplastic syndrome)

Increase in size of the cancerous lymph nodes, rash, and slight fever (Tumor flare reaction)

Brain damage which may cause headache, seizure, or blindness (leukoencephalopathy)

11.2 Expected Side Effects of Dexamethasone

Likely

- Increased appetite
- Weight gain
- Sleep disturbance
- Hypertension
- Fluid retention, ankle swelling
- Bruising
- Susceptibility to Infection
- Mood changes
- Slow wound healing
- Depression
- Hyperglycemia, which may lead to fatigue, weight loss, excessive thirst and frequent urination.

Less Likely

- Loss of appetite
- Muscle twitching
- Increased thirst, frequent urination
- Increased perspiration
- Diarrhea
- Nausea
- Headache
- Bone thinning
- Spinal fracture or fracture of bones
- Tachycardia
- Fungal infections

MEMORIAL SLOAN-KETTERING CANCER CENTER
IRB PROTOCOL

IRB#: 11-107A(12)

- Anxiety

Unlikely

- Blurred vision
- Personality changes
- Hypokalemia
- Swelling and/or redness of skin
- Allergic skin reactions
- Itching
- Hirsutism
- Muscle weakness or loss of muscle mass
- Rupture of tendons
- Menstrual cycle disturbances
- Facial puffiness, leading to the appearance of a “moon face” hormonal disturbances
- Hiccups.
- Development of diabetes

Rare but serious

- Stomach ulcers with bleeding that may cause hematemesis, blood in the stool and abdominal pain.
- Bowel perforation, irritation and bleeding of the esophagus
- Heart failure
- Allergic reaction that may lead to shortness of breath, abdominal cramps and hypotension
- Convulsions, brain swelling,
- Cataracts
- Glaucoma and increased blood pressure in the eye
- Pancreatic inflammation, abdominal swelling
- DVT or PE
- Aseptic necrosis of the hip

**12.0 CRITERIA FOR THERAPEUTIC RESPONSE/OUTCOME
ASSESSMENT**

Patients enrolled in this trial must have *asymptomatic* progression of disease only. The new baseline that will be used for comparison to assess the response to lenalidomide intensification with or without the addition of dexamethasone at 6 months will have to be established within two weeks prior to day 1 of cycle 1. Prior values will not be acceptable.

Patients' disease status at each data collection period will be evaluated based on the International Uniform Response Criteria. All disease responses, including after addition of dexamethasone, will be relative to the established baseline disease status within 2 weeks prior to day1 of cycle 1, i.e. prior to lenalidomide intensification.

MEMORIAL SLOAN-KETTERING CANCER CENTER
IRB PROTOCOL

IRB#: 11-107A(12)

International Uniform Response Criteria (modified)

Stringent Complete Response (sCR):

- sCR requires, in addition to CR (defined below), all of the following:
- Normal free light chain ratio (FLC).
- Absence of clonal cells in bone marrow by immunohistochemistry or immunofluorescence.

Complete Response (CR) requires *all* of the following:

- Absence of the original monoclonal paraprotein in serum and urine by routine electrophoresis and by immunofixation.
- Less than 5% plasma cells in a bone marrow aspirate and also on trephine bone biopsy, if biopsy is performed;
- No increase in size or number of lytic bone lesions on radiological investigations (development of a compression fracture does not exclude CR)*; and,
- Disappearance of soft tissue plasmacytomas.

**If not clinically indicated, radiographs are not required to document CR.*

Very Good Partial Response (VGPR) requires, in addition to PR (defined below), all of the following:

- Serum or urine paraprotein detectable by immunofixation but not on electrophoresis,
OR
- Greater than or equal to 90% reduction in serum paraprotein plus urine paraprotein <100 mg/24hrs.

Partial Response (PR) requires one of the following:

- Greater than or equal to 50% reduction in the level of the serum monoclonal paraprotein and/or reduction in 24 hour urinary monoclonal paraprotein either by greater than or equal to 90% or to <200 mg/24 hours in light chain disease.
- If the only measurable non-bone marrow parameter is FLC, greater than or equal to 50% reduction in the difference between involved and uninvolved FLC levels or a 50% decrease in level of involved FLC with 50% decrease in ratio,
- If the bone marrow is the only measurable parameter, greater than or equal to 50% reduction in bone marrow plasma cells given that the baseline count was greater or equal to 30%,
- Greater than or equal to 50% reduction in the size of soft tissue plasmacytomas (by radiography or clinical examination).

MEMORIAL SLOAN-KETTERING CANCER CENTER
IRB PROTOCOL

IRB#: 11-107A(12)

Minor Response (MR)

- $\geq 25\%$ to $\leq 49\%$ reduction in the level of serum monoclonal protein (SPEP)
- If present, a 50% to 89% reduction in 24-hour light chain excretion, which still exceeds 200 mg/24 hr.
- If the serum and urine M-protein are unmeasurable a $\geq 25\%$ to $\leq 49\%$ decrease in the difference between involved and uninvolved FLC levels is required in place of the M-protein criteria.
- 25% to 49 % reduction in the size of soft tissue plasmacytomas (by clinical or radiographic examination)

Stable Disease (SD)

- Patients who do not meet criteria for sCR, CR, VGPR, PR or progressive disease are considered to have stable disease (SD).

Progressive Disease (POD) requires one or more of the following:

- $>25\%$ increase in the level of the serum monoclonal paraprotein, which must also be an absolute increase of at least 0.5 g/dL.
- $>25\%$ increase in 24-hour urine protein electrophoresis, which must also be an absolute increase of at least 200 mg/24 hours.
- $>25\%$ increase in the difference between involved and uninvolved FLC levels (absolute increase must be >10 mg/dl),
- $>25\%$ increase in plasma cells in a bone marrow aspirate or on trephine biopsy, which must also be an absolute increase of at least 10%.
- Definite increase in the size of existing bone lesions or soft tissue plasmacytomas.
- Development of new bone lesions or soft tissue plasmacytomas.
- Development of hypercalcemia (corrected serum Ca >11.5 mg/dL or >2.8 mmol/L) not attributable to any other cause.

Note that the development of a compression fracture does not exclude continued response and may not indicate progression.

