1.7 Study Schema

2.0 OBJECTIVES AND SCIENTIFIC AIMS

Primary objective:

- To determine the overall response rate (CR, VGPR, PR, and MR) after 6 months of lenalidomide intensification administered initially at a dose of 25 mg orally days 1 to 21 of a 28 day-cycle, with or without the addition of dexamethasone, in patients with multiple myeloma found to have *asymptomatic* progression of their disease while on maintenance lenalidomide dose of 15mg mg daily or less.

Secondary objectives:

- To determine rates of \geq Grade 2 toxicity according to the Common Terminology Criteria for Adverse Events (CTCAE) Version 4.0
- To determine the overall response rate (CR, VGPR, and PR) at 6 months from initiation of lenalidomide intensification therapy of lenalidomide given as a single agent.
- To determine progression free survival: The PFS is defined as the time from registration to relapse/progression, death, initiation of non-protocol anti myeloma therapy, loss to follow up or end of study whichever comes first.
- To determine OS: The OS is defined as the time from registration to death, loss to follow-up or the end of the study, whichever comes first. Patients alive at the time of last observation are considered censored.

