6.0 CRITERIA FOR SUBJECT ELIGIBILITY

6.1 Subject Inclusion Criteria

Patients fulfilling the following criteria will be eligible for entry into this study:

- Patients must be 18 years of age or above at the time of enrollment.
- Patients must show evidence of *asymptomatic* relapse and/or progression of disease (increasing M spike in serum or urine by consensus criteria) while on lenalidomide maintenance after HDM/ASCT as part of initial line of therapy. Patients who have not had an HDM/ASCT as part of initial line of therapy but who are on continuous/maintenance lenalidomide after initial therapy will be permitted on study.
- Patient must have myeloma that is measurable by either serum or urine evaluation of the monoclonal component or by assay of serum free light chains. Measurable disease is defined as one or more of the following: serum M-protein ≥ 0.5 g/dl, urine M-protein ≥ 200 mg/24 h, and/or serum FLC assay: involved FLC level > 10 mg/dL with abnormal serum FLC ratio.
- Patients must have adequate organ function including: Hepatic function with Bilirubin $< 2x$ the upper limit of normal and ALT and AST $< 3x$ the upper limit of normal; renal function with creatinine clearance ≥ 60 ml/min using the Cockcroft-Gault formula; hematologic function as defined by an absolute neutrophil count > 1000 neutrophils per microliter, platelet $> 50,000$ platelets per microliter and hemoglobin of ≥ 9 gm/dL without transfusion support.
- All study participants must be registered into the mandatory Revlimid REMS® program, and be willing and able to comply with the requirements of the REMS® program.
- Females of child bearing potential (FCBP)¹ must adhere to the scheduled pregnancy testing as required in the Revlimid REMS® program. FCBP must have a negative serum

¹ A female of childbearing potential is a sexually mature female who: 1) has not undergone a hysterectomy or bilateral oophorectomy; or 2) has not been naturally postmenopausal for at least 24 consecutive months (i.e., has had menses at any time in the preceding 24 consecutive months).

MEMORIAL SLOAN-KETTERING CANCER CENTER IRB PROTOCOL

IRB#: 11-107A(12)

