14.0 BIOSTATISTICS

The primary objective of this study is to estimate overall response rate (\geq PR) to lenalidomide intensification with or without dexamethasone at 6 months. A single stage design that differentiates between response rates of 15% and 30% will be used to assess efficacy of lenalidomide intensification with or without dexamethasone.

The probabilities of a type I error (falsely accepting a non-promising therapy) and type II error (falsely rejecting a promising therapy) are set to 0.10 and 0.10, respectively. The null hypothesis response rate is based on the response rates ranging from 12.5% to 16.4% to the standard of care therapy in patients previously exposed to thalidomide who have relapsed or refractory disease (reference Webber and Dimopoulos papers^{38,39}). A total of 53 patients will be accrued. At the conclusion of the study, if a least 12 of the 53 patients respond by 6 months the treatment will be declared a success. At the end of the study, the response rate will be estimated and a confidence interval will be constructed.

We expect to accrue 53 patients in two years with approximately 10-15 patients accrued from MSKCC and the remaining patients accrued from the other centers.

The incidence of toxicities of grade 2 or higher toxicities (CTCAE version 4.0), the incidence of probable viral fungal and bacterial infections, and the incidence of treatment-related mortality, i.e., from causes other than relapse or progression, will be recorded for each patient after each cycle and at the end of study visit. Safety data will be described in a variety of ways, both graphically and in tabular form.

Progression free survival is defined as the time from treatment initiation to relapse/progression, death, initiation of non-protocol anti myeloma therapy, or last follow-up. Overall survival is defined as time from treatment initiation until death or last follow-up. Progression free and overall survival will be estimated using the Kaplan-Meier method.

We will estimate the response rate (CR, VGPR, and PR) by 6 months from initiation of lenalidomide intensification of lenalidomide given as single agent. For this calculation, patients who have asymptomatic progression after 2 cycles of lenalidomide and receive dexamethasone will be considered failures.

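### Partial response can be met by one unconfirmed value and, in light chain disease, by any fall below the 200 mg/24 h entry limit, which can inflate the count behind the 12-of-53 rule

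*Combined protocol and SAP*

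**What the plan says.** Section 14.0 gives the decision rule: "if a least 12 of the 53 patients respond by 6 months the treatment will be declared a success". There, and in section 1.6, a response is PR or better.

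Section 12.0 defines PR as a list of alternatives: "Partial Response (PR) requires one of the following". The serum, free light chain, marrow and plasmacytoma entries each need a fall of at least 50%. The urine entry needs a reduction "either by greater than or equal to 90% or to <200 mg/24 hours in light chain disease", and its second half carries no minimum percentage fall. No entry asks for a second or consecutive value.

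Section 6.1 accepts "urine M-protein ≥ 200 mg/24 h" as measurable disease, so the entry limit and the response threshold are the same number. Section 9.1 has response assessed after every 28-day cycle, which gives about six assessments by month 6. Section 12.0 takes baseline from the two weeks before cycle 1 and rules out earlier values. The Response Review part of section 16 makes responses subject to a central committee that works from submitted materials.

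**The concern.** Two features of the PR definition let measurement error count as response. First, one low value is enough. If any visit up to month 6 counts, a stable patient has about six chances to produce one. Second, a light chain patient whose urine protein sits just above 200 mg/24 h needs only a trivial drop to cross the line.

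A single-arm trial has no control group in which the same errors would appear, so false responses add directly to the count compared with 12. The question is how much room the rule has to absorb them.

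**Working it through.** **Design as stated.** Inputs from section 14.0: n = 53, success at 12 or more, null rate 0.15, alternative 0.30, both error limits 0.10.

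- Type I error = P(X ≥ 12 | 53, 0.15) = 0.0907.
- Power = P(X ≥ 12 | 53, 0.30) = 0.9094.

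The design reproduces, and 53 is the smallest sample size that meets both limits. The spare type I error is 0.10 − 0.0907 = 0.0093.

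**Effect of false PRs.** Let f be the share of true non-responders called PR (an assumption; the documents give none). The observed rate under the null is p = 0.15 + 0.85f.

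| f | p | Extra expected responders, 53 × 0.85f | Type I error |
|---|---|---|---|
| 0.3% | 0.1526 | 0.14 | 0.100 |
| 0.5% | 0.1543 | 0.23 | 0.107 |
| 1% | 0.1585 | 0.45 | 0.124 |
| 2% | 0.1670 | 0.90 | 0.164 |
| 3% | 0.1755 | 1.35 | 0.209 |

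If only the urine criterion misfires, f = (share of patients on that route) × (share of their non-responders who cross). With 5% and 5%, p = 0.15 + 0.85 × 0.0025 = 0.1521 and type I error is 0.098, inside the limit. With 10% and 20%, f = 2% and it is 0.164.

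**How often noise alone produces a PR.** Simulation with lognormal error around an unchanged true level, one baseline and six later values. The coefficient of variation (CV), the true level and the absence of growth are all assumptions.

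*Serum, at least one of six values 50% or more below baseline:* about 0% at CV 10%, 0.3% at CV 15%, 3.2% at CV 20%. With two consecutive values required: about 0.01% at CV 15% and 0.3% at CV 20%.

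*Urine, value below 200 mg/24 h, given a measured baseline of at least 200:*

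| True level (mg/24 h) | CV | One visit only | Any of six | Two consecutive |
|---|---|---|---|---|
| 210 | 10% | 31% | 89% | 35% |
| 210 | 20% | 40% | 95% | 51% |
| 230 | 10% | 8% | 40% | 3% |
| 230 | 20% | 24% | 81% | 23% |
| 250 | 10% | 1% | 7% | 0.1% |
| 250 | 20% | 13% | 57% | 7.5% |
| 300 | 10% | about 0% | about 0% | 0% |
| 300 | 20% | 2% | 12% | 0.2% |
| 400 | 20% | 0.02% | 0.1% | 0% |

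The urine effect fades quickly above about 300 mg/24 h. Very close to 200, confirmation alone does not remove it. Also requiring a 50% fall does: at 230 mg/24 h the any-of-six figure drops to about 0% (CV 10%) or 4% (CV 20%).

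**Cost of confirmation to power.** If confirmation loses 2% of true responders, p = 0.30 × 0.98 = 0.294 and power is 0.893. If it loses 5%, p = 0.30 × 0.95 = 0.285 and power is 0.865.

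**The case against.** The strongest objection is that the size of the effect is unproven, and that stands. A reader might infer that noise does inflate the count and breaks the 0.10 limit. The documents cannot show this, because they give none of the inputs that would fix f. Several points pull the figures down:

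- Patients enrol with progressing disease, so a flat true level is a pessimistic null. With an assumed 5% rise per month, serum halving at CV 20% falls from 3.2% to 0.8%, and crossing at 230 mg/24 h falls from about 40% to 4% (CV 10%) or from 81% to 38% (CV 20%). Section 4.1 also counts patients taken off study for progression within 6 months as failures.
- Urine progression in section 12.0 needs a rise of at least 200 mg/24 h. A patient entering on that rule at 205 or 230 would have risen from at most 5 or 30. Entry on another marker remains possible, but values this close to the limit may be uncommon.
- The text says both *by* and *at* 6 months. A single month-6 visit cuts serum halving at CV 20% to about 0.7%. It does not cure the urine criterion, where 8% to 24% still cross at 230 mg/24 h.
- The formula treats 15% as free of error. Section 14.0 derives it from observed rates of 12.5% to 16.4%. If those already include unconfirmed responses, the formula double-counts.
- Committee review may expose an isolated outlier. It is not a second measurement, and the committee would apply the same criteria, under which 195 mg/24 h qualifies.

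Two further inferences are tempting and not supported. One is that section 12.0 contradicts itself because a fall from 1000 to 250 mg/24 h (75%) is only a minor response while 205 to 195 is a PR. The minor response text covers the first case as written ("If present, a 50% to 89% reduction in 24-hour light chain excretion, which still exceeds 200 mg/24 hr"), and different cut-offs for different markers are not a contradiction. The other is that PR needs an absolute minimum change because progression has one. A fall from 0.5 to 0.25 g/dL is a true 50% fall, and nothing in the documents requires such a floor.

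**Conclusion.** The point holds as a gap in the endpoint definition. The written PR rule accepts one unconfirmed value and, in light chain disease, any fall below the entry limit, and no other section closes this. It can inflate the count behind the 12-of-53 decision, and the rule tolerates only about 0.3% miscounted non-responders before type I error reaches 0.10.

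Whether that tolerance is exceeded cannot be settled from the documents. The plausible range runs from no material effect (0.098 with 5% of patients on the urine route and 5% of their non-responders crossing) to a clear breach (0.164 with 10% and 20%). All of these rest on assumed error rates, assumed urine levels and, for the simulated crossing rates, a flat true level.

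Two related matters need separate reconciliation: *by* against *at* 6 months, and section 2.0, whose primary objective counts minor responses as well ("To determine the overall response rate (CR, VGPR, PR, and MR) after 6 months"). Adding minor response would not cure the gap, since single values would decide that category too.

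**What to change.** In sections 12.0 and 14.0, count PR or better for the primary endpoint only when it is met at two consecutive scheduled assessments. Confirm a response first seen at month 6 at the next scheduled test and date it to month 6. State how a response with a missing repeat value is counted.

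Report two sensitivity results: the unconfirmed count, and a count that also requires at least a 50% fall from baseline on the below-200 mg/24 h criterion. The second is needed because confirmation alone leaves a residue when urine protein lies very near 200.

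The change needs wording and programming only. The monthly tests already supply the repeat values, and no treatment rule is affected. The price is a slightly lower response rate, one more cycle before month-6 responders are classified, and some power. Power has as little slack as type I error (0.909 against 0.90), so section 14.0 should restate it under the confirmed definition, for example 0.893 or 0.865 if 2% or 5% of true responders fail to confirm.
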